Study protocol

Does investigator gender has an impact on patients perceived pain intensity after surgery?

Aim

The objective of this study is to investigate whether the gender of the investigator has an impact on patients reported levels of pain intensity after acute or scheduled surgery.

Background

Postoperative pain is a common problem after surgical procedures with many patients afflicted worldwide. Fundamental challenges are the complexity of measuring pain appropriately, and the many associated possible confounders. Over the last decades, gender of the investigator has been identified as a conceivable bias in the assessment and management of pain in experimental, as well as, clinical research. However, to our knowledge this issue has not so far been systematically investigated in a postoperative setting.

In a preclinical setting Levine et al. showed that male subjects reported less pain when evaluated by a female than by a male investigator, and this was followed by other similar studies indicating that the gender of the investigator may have an impact on the pain report Kallai et al. 2004, Gijsbers et al. 2005, Aslaksen et al. 2007 and Vigil et al. 2014. In a recent review Chapman et al. 2018 emphasize that it may have significant impact on experiments and clinical trials.

Methods

In this prospective paired cross-over study, two investigators of opposite gender independently obtain individually reported pain intensity levels in each study patient based on three different methods of pain assessment the Visual Analogue Scale (VAS), the Numeric Rating Scale (NRS), and the Painmatcher® (PM) technique based on electrical stimulation, at Malmö University hospital in Sweden.

Inclusion criteria is ongoing PACU care after recent surgery, age ≥ 18 years, cognitive and linguistic abilities to understand instructions and participate in the study, and perceived postoperative pain. All study participants receive oral and written study information and sign an informed consent form.

We have estimated to include around 50 patients per week, corresponding to around 600 patients in total, which we value to be enough margin verifying or rejecting the primary hypothesis of our study.

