In each study session – from arrival at the PACU until approximately 15-minutes after arrival – the patients shortly describe, in words of their own, the main character of their postoperative pain. Afterwards they rate their current pain intensity level with the three different study techniques (VAS, PM and NRS in mentioned order). The investigators inform the patients equally verbally on how to carry out the pain measurements and the patients were blinded to the study aim of evaluating potential impact of investigator gender. Additional information on surgical and anaesthetic procedures, including current analgesic medication, is obtained from the peri-operative database of the hospital, and from individual patient records.

Study value

To further improve the postoperative care and pain relieve after acute and scheduled surgery it is of great importance to study biological, psychological and social factors affecting patients pain perception. More knowledge and awareness of investigator gender would possibly encourage caretaking and treatment of patients with pain and further on improved pain relief.

Statistical analysis plan

Study data is recorded in a Microsoft Excel spreadsheet. Non-parametric statistical tests will be used to evaluate study data reflecting pain intensity due to Visual Analogue Scale (VAS), the Numeric Rating Scale (NRS) and the Painmatcher®. With the Painmatcher® we obtained three values at each evaluation and the mean of these will be used for comparison. Pain intensity levels will be evaluated with respect to influence of investigator gender with the Wilcoxon signed-ranked test for dependent samples. Pain intensity levels will be compared between female and male study participants with the Mann-Whitney *U*-test. Reported pain descriptors will be analysed with qualitative methods. As is common in statistical practice we will adopt a significance level of $P < 0.05$.

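### One primary hypothesis is assessed on three pain scales at an unadjusted P < 0.05, with no primary scale and no rule for turning three results into one conclusion

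*Combined protocol and SAP*

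**What the plan says.** The Aim section gives a single objective: "The objective of this study is to investigate whether the gender of the investigator has an impact on patients reported levels of pain intensity". The Methods section speaks of one hypothesis, in the singular, and describes the sample as large enough for "verifying or rejecting the primary hypothesis of our study".

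The design is a "prospective paired cross-over study" in which "two investigators of opposite gender independently obtain individually reported pain intensity levels in each study patient", using "three different methods of pain assessment": VAS, NRS and Painmatcher. The three are listed with equal standing.

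The Statistical analysis plan says that "Non-parametric statistical tests will be used to evaluate study data reflecting pain intensity" on these three scales. On the main question it says: "Pain intensity levels will be evaluated with respect to influence of investigator gender with the Wilcoxon signed-ranked test for dependent samples". The threshold follows at the end of the section: "As is common in statistical practice we will adopt a significance level of" P < 0.05.

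Neither the protocol nor the SAP names a primary scale, a composite, a testing order or a multiplicity adjustment. Neither says how many scales must be significant for the hypothesis to count as verified, or what to conclude if they disagree.

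**The concern.** P < 0.05 is a valid threshold for each test taken alone. The gap lies one step later: three results have to become one verdict on one hypothesis, and the plan does not say how. The false-positive rate of that verdict is therefore undefined. If any one significant scale is enough, it exceeds 5%. If all three are needed, it is below 5%. Should the scales disagree, whether the hypothesis was verified would depend on a choice made after the results are known.

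**Working it through.** **Inputs from the documents.** Three scales; one paired Wilcoxon test applied to pain intensity levels; significance level 0.05; around 600 patients.

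**Inputs assumed, because the documents do not give them.** One Wilcoxon test per scale; two-sided testing (the aim has no direction); an equal correlation ρ between the three test statistics; power per scale. The relevant ρ is driven by the within-patient differences between the two investigators, not by the ratings themselves.

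**The plan's own figure.** The total of around 600 is linked to around 50 patients per week (600/50 = 12 weeks). No power, effect size, standard deviation or dropout rate is stated, so the total cannot be reproduced as a power calculation, and power per scale has to be shown as a range.

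**Two statements that might seem to fill the gap.** The sequence VAS, Painmatcher, NRS in the protocol is the order in which patients are measured, not a testing hierarchy. Averaging the three Painmatcher values reduces that scale to one test; three scales remain.

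**Model.** Write each statistic as Z = μ + √ρ·W + √(1−ρ)·e, with W shared across scales and e separate for each scale, all standard normal. Given W = w, the chance that one scale is not significant is

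q(w) = Φ[(1.96 − μ − √ρ·w)/√(1−ρ)] − Φ[(−1.96 − μ − √ρ·w)/√(1−ρ)].

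Then P(at least one) = 1 − E[q³], P(all three) = E[(1 − q)³], and P(disagreement) = P(at least one) − P(all three).

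**Step 1: no effect (μ = 0).** At ρ = 0 the formula reduces to 1 − 0.95³ = 0.1426. For the overall verdict under Holm, 1.96 is replaced by 2.394 (two-sided 0.05/3 = 0.0167).

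| ρ | any one scale | all three | at least one after Holm |
|---|---|---|---|
| 0 | 14.3% | 0.01% | 4.9% |
| 0.5 | 12.5% | 0.3% | 4.5% |
| 0.8 | 9.8% | 1.4% | 3.5% |
| 0.95 | 7.3% | 3.0% | 2.6% |

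**Step 2: an effect present on all three scales.** Set μ = 1.960 + z(power), so 80% power gives μ = 1.960 + 0.842 = 2.802. Chance that one or two scales, but not none or all, are significant:

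| power per scale | ρ = 0.5 | ρ = 0.8 |
|---|---|---|
| 50% | 50% | 31% |
| 80% | 34% | 21% |
| 95% | 11% | 8% |
| 99% | 3% | 2% |

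**Step 3: what Holm costs.** With 80% power per scale, P(at least one significant) falls from 95.0% to 87.3% at ρ = 0.5 and from 90.0% to 79.5% at ρ = 0.8. The standardised paired difference detectable with 80% power, with 600 informative pairs, normal differences and Wilcoxon efficiency 3/π = 0.955 (600 × 0.955 = 573), is 2.802/√573 = 0.117 at level 0.05 and (2.394 + 0.842)/√573 = 3.236/√573 = 0.135 at level 0.0167.

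**Step 4: what requiring all three costs.** With 80% power per scale, P(all three) is 95.0 − 33.9 = 61.1% at ρ = 0.5 and 90.0 − 21.3 = 68.7% at ρ = 0.8.

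**The case against.** The strongest reply is that the inflation is conditional. The plan never says that one significant scale suffices, and an investigator who required all three would stay under 5%. That is right, and it rules out the stronger reading a reader might infer, that the trial has a false-positive rate of 14%. That figure needs both an any-one rule and uncorrelated tests, and the documents state neither.

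Low correlation is also hard to defend as the leading case. Stable patient pain cancels in the paired differences, so highly correlated ratings do not guarantee highly correlated tests. But any real change in pain between the two evaluations enters all three differences and pushes them together. The range 0.5 to 0.95 is the fairer one to lead with, and 14.3% is the upper end. Equal correlation is a simplification that matters little: with VAS and NRS at 0.9 and the other pairs at 0.5, the any-one rate is 10.8%.

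A reader might also infer that the scales will often disagree. The documents do not support this, because they state no power. Disagreement is common at 50% power and rare at 99%.

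Finally, the Wilcoxon sentence names no scale, so three separate tests are an inference. It is a reasonable one, since the SAP lists all three scales and defines no composite. What survives these objections is the missing rule itself, which depends on none of the assumed values.

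**Conclusion.** The concern holds in a limited form. Each test is valid at 0.05, but the verdict on the single primary hypothesis has no decision rule, and the stated 5% does not describe it. Under an any-one reading, which the plan leaves open, the two-sided false-positive rate is about 7% to 13% for correlations from 0.95 down to 0.5, and it exceeds 5% at every correlation below 1. Under an all-three reading it is at most about 3% over the correlations examined. These figures rest on one test per scale, two-sided testing and equally correlated normal test statistics. This should be corrected. It does not invalidate the design or the individual tests.

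The Mann-Whitney comparisons by patient sex answer a different question and are not part of this point. The past tense in the Painmatcher sentence of the SAP might be read as a sign that results had already been seen. One verb in a section written mostly in the future tense does not establish that; it matters only for the choice of remedy.

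**What to change.** Add to the SAP:

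- The investigator-gender hypothesis is tested by the Wilcoxon signed-rank test on VAS, NRS and Painmatcher, with Holm adjustment at a two-sided family-wise level of 0.05 (ordered p-values against 0.0167, 0.025 and 0.05).
- The hypothesis is verified if at least one scale is significant after adjustment and all scales significant after adjustment point in the same direction. For the overall verdict, the first condition is simply smallest p < 0.0167; the later Holm steps decide which further scales are named.
- Significant results in opposite directions are reported as inconsistent, not as verification.
- All three results are reported, whether significant or not.
- The Mann-Whitney comparisons by patient sex are secondary.

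Two alternatives are equally acceptable if the data have not been examined: name one primary scale that alone decides the hypothesis at two-sided 0.05 and test the others after it in a fixed order, or require all three to be significant. The choice is the sponsor's. If results have been seen, choosing a scale now is not prespecification, and Holm on all three has the advantage of needing no such choice.

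**Cost.** A few SAP sentences and no new data. Holm gives up the power shown in step 3 of the working. With a single primary scale, a positive result on another scale alone is only supportive. Requiring all three leaves the lower chance of success shown in step 4.
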